2.3. Study Plan

Throughout the study, blood samples will be collected to assess whether the study drug impacts the ability of the vaccine to elicit neutralizing antibody titers against the SARS-CoV-2 S protein, and to understand any impact on vaccine-induced humoral and cellular immune responses to various S protein epitopes. Additional details are provided in Section 9.2.3 of protocol.

Subjects will also have blood samples taken at select visits for drug concentration, immunogenicity, and exploratory analyses, and will be monitored for AEs [including Adverse Events of Special Interest (AESIs)] during in-person visits. For subjects in study arms 4 and 5

(receiving the study drug and vaccine on the same day), a phone call will be made within 24 hours following study drug and vaccine administration on day 1 for AE collection.

The last study visit will take place approximately 1 year after the first dose of the vaccine.

Figure 1: Study Flow Diagram (Enrollment Waves 1 and 2)

[figure not shown]
[figure not shown]

Figure 2: Study Flow Diagram (Enrollment Waves 3 and 4)

3. ANALYSIS POPULATIONS

In accordance with guidance from the International Conference of Harmonization of Technical Requirements for Registration of Pharmaceuticals for Human Use (ICH) guideline ICH E9 Statistical Principles for Clinical Trials ([ICH, 1998](#)), the following population of analysis will be used for all statistical analysis.

In this study, “as treated” is defined as: (1) subjects who receive study drug will be grouped in the vaccine + study drug combination arms (2) subjects who receive vaccine only will be grouped into the vaccine alone arm within the same randomization wave (e.g. for a subject randomized to arm 1 who receives vaccine only, they will be grouped into arm 6a).

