In addition to the above use case scenarios, the study will evaluate endogenous immune responses over time when 1200 mg IV of REGN10933+REGN10987 is administered 6 days after the first dose of Moderna mRNA-1273 (ie, study day 7). This interval was chosen to allow adequate

production and presentation of S protein antigens following vaccination and is thus intended to represent a scenario in which the immune system is “primed” prior to treatment with REGN10933+REGN10987. This will allow for assessment of safety of REGN10933+REGN10987 administration in close temporal proximity to vaccination. In the event REGN10933+REGN10987 is found to interfere with the endogenous immune response to vaccination when given prior to or concomitantly with vaccination, this will allow assessment of whether, in the prophylaxis setting, vaccination prior to REGN10933+REGN10987 administration will allow high risk subjects to receive both long term and short term protection from vaccination and REGN10933+REGN10987 administration followed shortly thereafter.

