7. Note that not all subjects will receive study drug at randomization. Refer to Section 8.5 and Figure 1 for more information.

Study arms 4 and 5: Subjects assigned to study arms 4 and 5 will receive both the study drug and vaccine on day 1. The study drug will be administered first, followed by the vaccine. There must be a minimum of 2 hours waiting period between administration of the study drug and subsequent vaccine administration. Approximately 24 hours after completion of the study drug and vaccine administration on day 1, subjects will be followed up by telephone for safety. Subjects should be monitored for at least 1 hour after study drug or vaccine administration.

Study arms 6a, 6b, 6c, and 6d only: Subjects assigned to one of these study arms will not receive study drug. These subjects will receive the vaccine only. These subjects should be monitored for at least 30 minutes after vaccine administration.

Refer to Section 9.2.2 for additional information concerning administration and monitoring requirements following study drug and/or vaccine administration.

8. Serology characterization assays will be used to assess antibodies against various SARS-CoV-2 antigens including: S protein, RBD, S1, and N protein. Refer to Section 9.2.3.1, Section 9.2.3.2, and Section 9.2.3.3 for more information on procedures and assays related to vaccine response assessment.
9. Vital signs, including temperature, blood pressure, heart rate, and respiratory rate will be collected prior to and 30 minutes following each administration of the study drug or vaccine primary series (first and second dose) as described in Section 9.2.4.1.
10. Actual dosing time and drug concentration sample collection times will be recorded.

Study arms 1, 2, 3, 7, 8, and 9 (receiving IV infusion of study drug): At the indicated visit, blood for assessment of drug concentration in serum will be taken prior to dosing and within 60 minutes after the end of infusion (EOI). The EOI sample should be collected from the arm contralateral to that used for IV infusion. If not medically feasible, the EOI sample can be drawn from the same arm, but not from the infusion catheter.

Study arms 4 and 5 (receiving SC injection of study drug): At the screening/baseline visit, blood for assessment of drug concentration in serum will be taken prior to dosing. The post-dose blood collection should occur at least 1 hour after study drug administration.

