11.3. Analysis Sets

11.3.1. Vaccine Response Analysis Sets

The **modified full analysis set (mFAS)** includes all randomized subjects who have been vaccinated with at least one dose and have a negative serology test result from the central laboratory test at baseline; it is based on the treatment received (as treated).

The **per protocol set (PPS)** includes all randomized subjects who have been vaccinated with at least one dose and do not meet the PPS exclusion criteria; it is based on the treatment received (as treated).

The PPS excludes subjects who:

- Receive positive SARS-CoV-2 serology result based on central laboratory test at baseline
- Do not receive the second dose of the vaccine
- Receive a positive diagnostic test result for SARS-CoV-2 infection before 56 days after the first dose of the vaccine
- Receive any dose of a coronavirus vaccine (refer to Section 8.8.1) outside of the study within 56 days after the first dose of the vaccine
- Receive systemic immunosuppressants or immune-modifying drugs within 56 days after the first dose of the vaccine
- Receive IVIG or blood products within 56 days after the first dose of the vaccine

The SAP will document the finalized exclusion criteria for the PPS.

The PPS is the primary analysis set for assessing vaccine response.

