2. INVESTIGATION PLAN

2.1. Study Design and Randomization

This study is a phase 2, randomized, open-label, parallel group study in healthy adult volunteers to assess the immunogenicity, safety, and tolerability of Moderna mRNA-1273 vaccine when administered with REGN10933+REGN10987.

At screening, eligible subjects were to be assigned to an enrollment wave. The enrollment waves were intended to avoid or minimize the potential for unused doses of Moderna mRNA-1273 COVID-19 vaccine (Protocol Section 3.2.1 for additional rationale). Every effort was made by sites to avoid unused doses of vaccine.

Every effort was made by the site to ensure balance of age (<65 years and \geq 65 years) within each of the enrollment waves. At baseline (day 1), subjects were to be randomized to the corresponding study arms in each wave as described in [Table 1](#).

Randomization was performed according to a computer-generated randomization scheme provided by an interactive web response system (IWRS) to a designated study pharmacist or a qualified designee.

Randomization was stratified by age (<65 years versus \geq 65 years).

Table 1: Study Treatment Assignment

Study Arm	Randomization Ratio	Targeted Enrollment	Co-administered REGN10933+REGN10987 Combination Therapy	Moderna mRNA-1273 Vaccine*
Enrollment Wave 1				
1	2	30	1200 mg (600 mg of each mAb) IV on day 1	On day 15 and day 43
2	2	30	300 mg (150 mg of each mAb) IV on day 1	On day 15 and day 43
3	2	30	150 mg (75 mg of each mAb) IV on day 1	On day 15 and day 43
6a	1	15	None	On day 15 and day 43
Enrollment Wave 2				
4	2	30	1200 mg (600 mg of each mAb) SC on day 1	On day 1 and day 29
5	2	30	600 mg (300 mg of each mAb) SC on day 1	On day 1 and day 29
6b	1	15	None	On day 1 and day 29
Enrollment Wave 3				
7	15	30	48 mg (24 mg of each mAb) IV on day 1	On day 15 and day 43
8	15	30	12 mg (6 mg of each mAb) IV on day 1	On day 15 and day 43
6c	4	8	None	On day 15 and day 43
Enrollment Wave 4				
9	15	30	1200 mg (600 mg of each mAb) IV on day 7	On day 1 and day 29

6d	4	8	None	On day 1 and day 29
----	---	---	------	---------------------

*Moderna mRNA-1273 vaccine will be administered as described on the US FDA EUA HCP Fact Sheet, 2021)
mAb=monoclonal antibody; SC=subcutaneous; IV=intravenous.

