3.1. Per Protocol Set Analysis Set (PPS)

The per protocol set (PPS) includes all randomized subjects who have received both doses of vaccine and who do not meet the following exclusion criteria:

1. Have a positive SARS-CoV-2 central serology result prior to the first dose of vaccine.
2. Receive a positive Reverse Transcription Polymerase Chain Reaction (RT-PCR) diagnostic test result for SARS-CoV-2 infection at any time point prior to the scheduled visit 56 days after the first dose of vaccine.
3. Receive any dose of investigational or approved passive antibodies for SARS-CoV-2 infection prophylaxis (eg, convalescent plasma or sera, mAbs, hyperimmune globulin) outside of the study at any time point prior to the scheduled visit 56 days after the first dose of vaccine.
4. Receive any other vaccine within 28 days prior to the study to the scheduled visit 56 days after the first dose of Moderna mRNA-1273 vaccine administered as part of this study.

Exception: seasonal influenza vaccine is only prohibited within 14 days before or after study drug administration, or within 14 days before or after Moderna mRNA-1273 vaccine administration.

5. Receive systemic medications that suppresses the immune system (for corticosteroids, ≥ 20 mg/day of prednisone equivalent) at any time point prior to the scheduled visit 56 days after the first dose of vaccine.
6. Receive IVIG or blood products at any time point prior to the scheduled visit 56 days after the first dose of vaccine.
7. Subjects with incomplete infusions or injections of study drug or vaccine at any time point prior to the scheduled visit 56 days after the first dose of vaccine.
8. Subjects with baseline neutralization antibody titer above the lower limit of quantification (LLOQ).

The PPS is the primary analysis set for assessing vaccine response related endpoints.

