3.3. Randomized Analysis Set

The randomized analysis set includes all randomized subjects; it is based on the treatment allocated by the IWRS (as randomized).

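### The as-treated rule can move a never-infused arm 9 subject into the vaccine-only control because of events after the first vaccine dose, mainly in the safety set and mFAS

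*SAP*

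**What the plan says.** SAP section 3 sets the as-treated rule for the whole study: "subjects who receive vaccine only will be grouped into the vaccine alone arm within the same randomization wave". Its worked example is that "for a subject randomized to arm 1 who receives vaccine only, they will be grouped into arm 6a". By the same rule an uninfused arm 9 subject goes to arm 6d.

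The rule applies to these sets:

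- The mFAS (SAP 3.2) and the safety set (SAP 3.4) are expressly as treated.
- Protocol 11.3.1 makes the PPS as treated too; it covers subjects who "do not meet the PPS exclusion criteria; it is based on the treatment received (as treated"). SAP 3.1 does not repeat this and names no other grouping.
- SAP 3.1 requires both vaccine doses for the PPS. Its criterion 7 excludes "Subjects with incomplete infusions or injections of study drug or vaccine" up to the day-56 visit.
- SAP 3.3 defines a Randomized Analysis Set, of which it says "it is based on the treatment allocated by the IWRS (as randomized"). No safety or vaccine-response analysis is assigned to it.

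The order of dosing differs by arm. In arms 1, 2, 3, 7 and 8, drug is given on day 1 and the first vaccine dose on day 15. In arms 4 and 5 both fall on day 1: "The study drug will be administered first, followed by the vaccine". In arm 9 the drug is "1200 mg (600 mg of each mAb) IV on day 7" (SAP Table 1), that is, "administered 6 days after the first dose of Moderna mRNA-1273 (ie, study day 7") (Protocol 3.2.1.1).

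**The concern.** In every arm but arm 9, whether a subject receives drug is settled before the first vaccine dose, so a reaction to that dose cannot change the subject's group. In arm 9 it can. Someone who reacts to the vaccine or falls ill in days 1 to 6, and for that reason is not infused, leaves arm 9 and joins the control.

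During days 1 to 6 every arm 9 subject has had vaccine only. The as-treated rule then sorts events from those days by what happened later: those of subjects who go on to be infused count under the combination, and those of subjects who do not count under vaccine alone. Days 1 to 6 lie inside the primary series vaccination period (SAP 4.6.1), so these events enter the tables by treatment group.

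Protocol 3.2.1.1 gives the safety of dosing close to vaccination as one purpose of arm 9. The rule can take early reactors out of that arm and put them into its comparator, so that the combination looks safer, and vaccine alone worse, than the randomised groups would show.

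**Working it through.** **Inputs.** Each drug arm has 30 planned subjects. Controls are 15 + 15 + 8 + 8 = 46, of whom 8 are in arm 6d (SAP Table 1). The assumed log10 SD is 0.30 (Protocol 11.2). The documents give no rate of missed day-7 infusions and no titre difference for such subjects, so both are assumptions below.

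**The plan's own precision figure.** The ANCOVA has nine treatment groups and one age slope, so df = 286 - 10 = 276 and t = 1.969. The half-width for 30 against 46 is 1.969 × 0.30 × √(1/30 + 1/46) = 0.139, which matches the stated 0.14. Regrouping hardly changes it.

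**Safety, assumed illustration.** Suppose 2 of 30 arm 9 subjects react to the first vaccine dose and miss the infusion, and no one else in arm 9 or the controls reacts.

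| Grouping | Arm 9 | Pooled control | 6d alone |
|---|---|---|---|
| As randomised | 2/30 (6.7%) | 0/46 | 0/8 |
| As treated | 0/28 | 2/48 (4.2%) | 2/10 (20%) |

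The direction of the comparison reverses with either control.

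**Titre.** Let k of 30 arm 9 subjects be uninfused, with log10 titres d above the rest of the arm. Assume no drug effect, so that the as-randomised difference is 0.

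- Mean of the remaining arm 9 subjects: -kd/30.
- Mean of the moved subjects: d(1 - k/30).
- Bias if they are excluded: -kd/30.
- Bias if they are moved into a control of size C: -kd/30 - k·d(1 - k/30)/(C + k).

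For k = 1, d = 0.30 (one SD) and C = 46: -0.010 - 0.29/47 = -0.016. For 6d alone (C = 8): -0.010 - 0.29/9 = -0.042.

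| k, d = 0.30 | Excluded | Moved, pooled control | Moved, 6d alone |
|---|---|---|---|
| 1 | -0.010 | -0.016 (-3.7%) | -0.042 (-9.3%) |
| 2 | -0.020 | -0.032 (-7.0%) | -0.076 (-16.1%) |
| 3 | -0.030 | -0.047 (-10.2%) | -0.104 (-21.2%) |

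Percentages are changes in the geometric mean ratio. Halving d halves the log10 values, and a negative d reverses their sign. The optional analysis within waves 3 and 4 (SAP 5.7.5) has 8 + 8 = 16 planned controls; one moved subject there gives -0.010 - 0.29/17 = -0.027.

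**Who can reach the PPS control.** A subject without a second vaccine dose is out; under Protocol 8.3.3 this includes anyone with a related allergic reaction of grade 3 or higher. A positive RT-PCR (criterion 2) or systemic immunosuppression (criterion 5) before the day-56 visit also excludes. What is left is the never-infused subject who completes both doses and meets no other exclusion, provided that criterion 7 does not apply.

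**The case against.** The strongest reply is that safety by actual exposure is a prespecified choice in both documents, and that a subject who was never infused did have vaccine-only exposure. The study tests no hypotheses. Causality is assessed separately for drug and vaccine (Protocol 10.2.5), related events are tabulated separately (SAP 5.8.1), and SAP 5.5 lists subjects whose treatment differs from allocation. All of this stands: the as-treated table is legitimate and the moved subjects can be identified. A listing, however, does not restore the randomised comparison.

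A reader might infer more than the documents support in four ways:

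- *That the primary titre analysis is broadly compromised.* The PPS exclusions block most routes, and the bias against the pooled control is small for one or two subjects. Its direction is unknown.
- *That the SAP knowingly drops partial infusions and keeps missed ones.* Criterion 7 can be read to cover an infusion that never started. It is ambiguous. The section 3 example points towards regrouping but is not specific to the PPS.
- *That the control rate would be distorted to 20%.* That figure takes 6d alone as comparator, with assumed rates. SAP 5.7.1 pools the vaccine-alone arms for all analyses. The sentence sits under the primary response variable, so its reach to safety is arguable, but SAP 5.8 does not specify a comparison with 6d alone.
- *That the Randomized Analysis Set is unused.* SAP 5.5 gives disposition counts for each analysis set. It is safety and response analyses that do not use it.

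It is also fair to say that excluding these subjects from the PPS is still selection after randomisation. The Excluded column of the table shows what remains.

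**Conclusion.** The point holds in a limited form. The rule is explicit, and arm 9 is the one arm where it can transfer a subject to control because of events after the first vaccine dose. The main exposure is in the safety set, and in the mFAS if response is explored there (optional under SAP 5.7.4). The PPS is exposed only through a narrow route that criterion 7 leaves unclear.

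The size is unknown and probably small. One moved subject at one SD gives a pooled titre bias of 0.016/0.14, about 11% of the confidence interval half-width. In the safety illustration two subjects are enough to reverse the direction, but that rests on assumed counts and on no other reactions. The precision figures in the plan are correct and unaffected. This is a cheap improvement, not a threat to the primary result.

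**What to change.** - In SAP 3.1, criterion 7, state that subjects randomised to a drug arm who receive no study drug are excluded from the PPS and are not regrouped as controls. Protocol 11.3.1 leaves the final PPS criteria to the SAP. This reduces the bias but does not remove it: for one subject at one SD, from -0.016 to -0.010 log10.
- Add one supplementary safety table with arm 9 and the vaccine-alone controls grouped as randomised from day 1, next to the as-treated table, and state there whether the controls are pooled.
- Show any mFAS vaccine-response analysis with the same as-randomised grouping next to the as-treated output.

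The cost is SAP wording, a little extra output and the loss of a few subjects from the PPS. No new data are needed and clinical conduct does not change.

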3.1. Per Protocol Set Analysis Set (PPS)

The per protocol set (PPS) includes all randomized subjects who have received both doses of vaccine and who do not meet the following exclusion criteria:

1. Have a positive SARS-CoV-2 central serology result prior to the first dose of vaccine.
2. Receive a positive Reverse Transcription Polymerase Chain Reaction (RT-PCR) diagnostic test result for SARS-CoV-2 infection at any time point prior to the scheduled visit 56 days after the first dose of vaccine.
3. Receive any dose of investigational or approved passive antibodies for SARS-CoV-2 infection prophylaxis (eg, convalescent plasma or sera, mAbs, hyperimmune globulin) outside of the study at any time point prior to the scheduled visit 56 days after the first dose of vaccine.
4. Receive any other vaccine within 28 days prior to the study to the scheduled visit 56 days after the first dose of Moderna mRNA-1273 vaccine administered as part of this study.

Exception: seasonal influenza vaccine is only prohibited within 14 days before or after study drug administration, or within 14 days before or after Moderna mRNA-1273 vaccine administration.

5. Receive systemic medications that suppresses the immune system (for corticosteroids, ≥ 20 mg/day of prednisone equivalent) at any time point prior to the scheduled visit 56 days after the first dose of vaccine.
6. Receive IVIG or blood products at any time point prior to the scheduled visit 56 days after the first dose of vaccine.
7. Subjects with incomplete infusions or injections of study drug or vaccine at any time point prior to the scheduled visit 56 days after the first dose of vaccine.
8. Subjects with baseline neutralization antibody titer above the lower limit of quantification (LLOQ).

The PPS is the primary analysis set for assessing vaccine response related endpoints.

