The primary endpoint will be assessed during the vaccine response assessment period, which includes the first 56 days after the first dose of Moderna mRNA-1273 (Section 4.1 and Section 6.1.1). SARS-CoV-2-neutralizing antibodies induced by Moderna mRNA-1273 vaccine can be detected as early as 2 weeks after the first vaccine dose, with titers peaking on day 36 (35 days after the first dose and one week after the second dose of the vaccine), and remaining at peak levels at day 57 and day 119 (pseudovirus serum neutralizing infectious dose 50 [ID₅₀] titers between 256 to 1024) (Jackson, 2020) (Widge, 2021). Assessing the primary endpoints after 56 days of the first dose of vaccine will thus maximize the ability to detect the effect of mAb administration on vaccine responses (Jackson, 2020). Additional analyses of neutralizing antibody titers at approximately 6 months, 9 months, and 1 year after vaccine administration will assess long-term/memory immune response to SARS-CoV-2 following vaccination with Moderna mRNA-1273.

An open-label design was chosen for this study, as it is considered appropriate and sufficient for achieving the primary objective, as well as the other pharmacodynamic objectives, of the study.

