8.3.3. Vaccine Deferral or Discontinuation

In subjects who become infected, the timing of vaccine administration (either the first dose, second dose, or booster dose, as applicable) should be deferred according to the most recent CDC guidance ([CDC, 2021](#)). Subjects who become pregnant will be counseled accordingly.

For applicable vaccine discontinuation rules, always refer to the latest Moderna mRNA-1273 vaccine EUA Fact Sheet ([Moderna COVID-19 Vaccine \[HCP Fact Sheet\], 2022](#)).

Vaccination will be permanently stopped or not administered in the event of:

- Serious or severe allergic reactions (grade ≥ 3) considered related to REGN10933+REGN10987 or Moderna mRNA-1273 vaccine

Note: In case of mild to moderate allergic reactions (grade ≤ 2) considered related to REGN10933+REGN10987 or Moderna mRNA-1273 vaccine, vaccine discontinuation is up to the investigator's discretion.

- Subject withdrawal of consent

Subjects who permanently discontinue from Moderna mRNA-1273 vaccine should be encouraged to remain in the study. Those who agree and do not withdraw from the study will be asked to return to the clinic for all remaining study follow up visits per the Schedule of Events.

Subjects who permanently discontinue and who opt to withdraw from the study will be asked to complete study assessments described in Section [9.1.2](#).

If a subject requires a prohibited medication (Section [8.8.1](#)) at any time during the study, the principal investigator should contact the Sponsor medical monitor (except for illness requiring prompt treatment). Based on the discussions, vaccination may either be continued or permanently discontinued.

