5.6. Extent of Study Treatment Exposure and Compliance

The number of subjects whose infusion of REGN10933+REGN10987 or whose injection of vaccine was interrupted or incomplete will be tabulated by treatment group for the SAF.

The number of injections of primary series vaccine will be tabulated by treatment group for the SAF. Among those with more than one injection of vaccine, the time between first and second vaccination will be tabulated by treatment group for the SAF. The number of subjects with injections of booster vaccine will be tabulated by treatment group. Time from second injection of primary series vaccine to booster vaccine injection will be tabulated by treatment group for the SAF.

The extent of follow-up (completing visit 56 days after the first vaccine dose, visit 52 weeks after the first vaccine dose) will be tabulated by treatment group for the SAF.

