6.4. Analysis Windows

Assessments repeatedly collected during the study will be defined by the eCRF visit label for temporal tabulations and subject listings.

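### The primary analysis set does not require dose 2 to precede the day-56 sample, so a titre drawn before a very late dose 2, or within about a week after it, can count as the primary endpoint

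*SAP*

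**What the plan says.** The per protocol set (PPS) is the primary set for vaccine response. SAP 3.1 opens: "The per protocol set (PPS) includes all randomized subjects who have received both doses of vaccine and who do not meet the following exclusion criteria". The counterpart in Protocol 11.3.1 removes subjects who "Do not receive the second dose of the vaccine". Neither text dates dose 2 or relates it to the primary sample.

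Of the eight exclusions in SAP 3.1, numbers 1 and 8 concern status before vaccination. Numbers 2 to 7 are each tied to the scheduled day-56 visit, but none concerns the timing of dose 2. The nearest is criterion 7, which runs up to the visit counted from dose 1 and reads in part: "Subjects with incomplete infusions or injections of study drug or vaccine at any time point prior to the scheduled visit 56 days after the first". SAP 5.6 uses the same word for an administration that was cut short, counting subjects "whose injection of vaccine was interrupted or incomplete will be tabulated by treatment group for the SAF".

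SAP 5.7.1 counts the endpoint from dose 1 (study day 71 or 57, by arm). For placing samples, SAP 6.4 says: "Assessments repeatedly collected during the study will be defined by the eCRF visit label for temporal tabulations and subject listings". SAP 5.6 adds that, for subjects with more than one injection, "the time between first and second vaccination will be tabulated by treatment group for the SAF". No analysis set uses that interval, and the interval from dose 2 to the sample is not tabulated.

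Protocol 3.2.1.3 justifies day 56 by the response curve, with "titers peaking on day 36 (35 days after the first dose and one week after the second dose of the vaccine") and peak levels still present at days 57 and 119.

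**The concern.** The day-56 titre is meant to lie on the plateau after two doses. The stated rules do not ensure this for a subject whose second dose is very late. In arm 1, dose 2 is planned for study day 43 and the primary sample for day 71. If dose 2 is given on day 68, the day-71 sample is taken 3 days after it. If dose 2 is given on day 80, the day-71 sample is a one-dose titre. Both subjects have received two doses, meet no exclusion on that account, and carry the right visit label.

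A low titre of this kind in a study-drug arm would look like interference with the vaccine. In the pooled vaccine-alone group it would hide interference. The study is open-label (Protocol 8.6), so leaving such cases to be settled after the data are seen means excluding subjects with the arm known.

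**Working it through.** **Inputs.** SD 0.30 log10, 30 subjects per study-drug arm, 46 pooled controls and half-width 0.14 (Protocol 11.2, SAP 2.2). Dose 2 planned 28 days after dose 1 (Protocol 6.1). Dose-2 visit window -1 to +3 days and day-56 visit window ±2 days (Protocol 9.1). Peak one week after dose 2 (Protocol 3.2.1.3). The documents give neither a one-dose titre nor a rate of late second doses.

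**1. The plan's own precision.** Half-width = t × SD × √(1/n1 + 1/n2). With 74 degrees of freedom, 1.993 × 0.30 × √(1/30 + 1/46) = 0.140. The stated 0.14 is reproduced.

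**2. Dose 2 to sample when both visits are in window.**
- Waves 1 and 3: dose 2 on study days 42 to 46, sample on days 69 to 73. Shortest 69 − 46 = 23 days, longest 73 − 42 = 31.
- Waves 2 and 4: dose 2 on days 28 to 32, sample on days 55 to 59. Again 55 − 32 = 23 to 59 − 28 = 31.

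**3. How late dose 2 must be** (days counted from dose 1).
- Dose 2 less than 7 days before the nominal sample: given after day 56 − 7 = 49, so more than 49 − 28 = 21 days late.
- Sample is a one-dose titre: dose 2 about 56 − 28 = 28 days late, or 54 − 28 = 26 for the earliest in-window sample.

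**4. Size, by assumption.** Let an affected titre lie d = 0.5, 1.0 or 1.5 log10 below the two-dose plateau. With k such subjects in an arm of 30, the mean shifts by k × d / 30. The geometric mean changes by 10^(−shift) − 1.

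| d (log10) | k = 1: shift (change) | k = 3: shift (change) | k that shifts by 0.14 = 0.14 × 30 / d |
|---|---|---|---|
| 0.5 | 0.017 (−3.8%) | 0.05 (−10.9%) | 8.4 |
| 1.0 | 0.033 (−7.4%) | 0.10 (−20.6%) | 4.2 |
| 1.5 | 0.050 (−10.9%) | 0.15 (−29.2%) | 2.8 |

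One affected control shifts the pooled mean by d / 46, from 0.5/46 = 0.011 to 1.5/46 = 0.033. That shift enters all eight comparisons in the opposite direction.

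**5. A 14-day minimum.** It is twice the 7 days to peak and below the 23-day in-window minimum, so it excludes nobody dosed and sampled within the schedule windows. For a nominal day-56 sample it removes subjects whose dose 2 fell after day 56 − 14 = 42, that is, more than 14 days late.

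**The case against.** The case on the other side is strong on frequency and size, and much of it stands.

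- **The written route to a late dose is mostly closed.** Protocol 8.3.3 says "the timing of vaccine administration (either the first dose, second dose, or booster dose, as applicable) should be deferred", but only for subjects who become infected. SAP 3.1 criterion 2 removes anyone RT-PCR positive before the day-56 visit, and swabs are scheduled throughout the response period. This stands. What is left is infection shown only by another test (Protocol 11.3.1 refers to any positive diagnostic test, the SAP only to RT-PCR), missed visits and schedule deviations. Protocol 6.1.2 keeps subjects with suspected or confirmed COVID-19 on their original schedule. For other delays the documents do not say whether the day-56 visit would move.
- **The delay must be extreme.** Against a window of −1 to +3 days, more than three weeks is a gross deviation, and on the protocol's own kinetics a moderate delay matters little. This stands.
- **SAP 5.6 would reveal late doses.** It would, through the interval between doses. It would not remove an affected sample from the primary analysis.
- **Criterion 7 might cover a dose not given by day 56.** Its wording and SAP 5.6 point to an interrupted or partial administration, so this reading fails.
- **A new rule adds a post-randomization exclusion.** This stands and calls for a sensitivity analysis.
- **The study is descriptive, with no hypothesis test.** True. Only estimates and intervals are affected.

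A reader might infer from Protocol 8.3.3 that delay would fall only in study-drug arms, because vaccination after a mild or moderate drug reaction is left to the investigator. The text does not support this. The discretion is over discontinuing the vaccine, not delaying it, and it also covers reactions to the vaccine, which controls can have. A subject who discontinues before dose 2 is outside the PPS already.

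A reader might also make something of the extra dose-1 window in waves 1 and 3. The interval from dose 2 to sample is 23 to 31 days in every wave. Nor should one affected subject be read as widening that arm's interval greatly: SAP 5.7.1 fits one ANCOVA to all groups, and with the usual common residual variance the effect is small.

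**Conclusion.** The gap in the text is real. The PPS does not time dose 2, the endpoint is counted from dose 1, and samples are placed by label. Applied as written, the rules accept a value that the plateau rationale does not cover.

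The effect is small unless several subjects in one arm are affected. One subject of 30 moves the arm mean by 0.017 to 0.05 log10, and about three to eight would be needed to move it by the stated half-width of 0.14. These figures rest on the assumed deficit of 0.5 to 1.5 log10. The number of affected subjects is also unknown and may be zero. A reader might infer that one-dose titres did enter the primary analysis; the documents show only that the rules would allow it. This is a cheap improvement, not a threat to the main result.

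**What to change.** All changes are to the SAP. Protocol 11.3.1 already leaves the final PPS exclusions to it. No visit, dose or vaccination rule changes.

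1. **SAP 3.1:** add that dose 2 must precede the primary endpoint sample by a pre-specified minimum interval, by actual dates, and that otherwise the subject is excluded from the PPS day-56 analysis. Fourteen days is one workable choice.
2. **SAP 6.4 and 5.6:** derive days from dose 2 to the primary sample. Tabulate them by arm, with any exclusions under the new rule, beside the dose 1 to dose 2 interval already planned.
3. **SAP 5.7.4:** commit to running the primary analysis in the mFAS as a sensitivity check on the new exclusion; at present that use of the mFAS is only optional. The two sets differ in other ways too, so the tabulated exclusions are needed to read any difference.

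The cost is one sentence, one derived variable, one table and one repeat of a planned model. The downside is that a subject with a very late dose 2 leaves the primary set. With a 14-day minimum this includes a few who may already have reached the stated one-week peak. Such a subject stays in the mFAS if seronegative at baseline by the central test. The loss is affordable, since Protocol 11.2 already considers 50% exclusion and gives a half-width of 0.20 for that case.
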